4.2 Study Population

The Mother-baby link includes 1,071,379 children born from Jan 1st 1990 to June 30th 2016.

Inclusion Criteria:

- Children whose mother was prescribed an only monotherapy of macrolide or penicillin during pregnancy (between 5 Gestational Week [GW] and delivery)
- Children who registered with the general practice (GP) within 6 months of birth
- Children whose mother was aged 14 to 50 years at delivery and had been registered with GP from at least 50 weeks before estimated conception date to delivery

Exclusion Criteria:

Children with known chromosomal abnormalities or with fetal exposure to known teratogenic medications (warfarin, angiotensin-converting enzyme (ACE) inhibitors, antineoplastic agents, isotretinoin, misoprostol, and thalidomide).

Children will be followed from birth to death, end of follow-up (June 30th, 2016), or age 14, whichever came first.

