4.3.2 Outcome

Based on previous evidence from experimental and epidemiological studies, we hypothesized that short-term fetal hypoxia induced by fetal arrhythmia could possibly be the underlying mechanism of observed adverse effects of macrolides.(22) We therefore include outcomes which could potentially result from short-term fetal hypoxia, i.e. neurodevelopmental disorders (CP, epilepsy, attention-deficit/hyperactivity disorder (ADHD) and autism spectrum disorder (ASD)) and major congenital malformation (malformation overall and system-specific malformations).

Neurodevelopmental disorders (CP, epilepsy, ADHD and ASD) are defined as the time to the first Read code or prescription indicating the outcomes by 14 years old. We have identified CP cases from informative prescription or Read codes using the Random Forest approach and were validated by a paediatric-neurologist blinded to the prenatal antibiotics exposure.(23) Other neurodevelopmental disorders (epilepsy, ADHD and ASD) will be identified with previously validated criteria using diagnostic codes and/or prescriptions (table 1). (24-26)

Major malformations will be identified from the European Surveillance of Congenital Anomalies (EUROCAT).(27) We will exclude musculoskeletal malformations (e.g. Club foot, knock-knee and hip dislocation) because they are not reliably recorded in GP records.(28) We also exclude children with known chromosomal abnormalities and children whose mother were exposed to known teratogenic medications (warfarin, angiotensin converting enzyme (ACE) inhibitors, antineoplastic agents, isotretinoin, misoprostol, and thalidomide). Any of the remaining 11 system-specific malformations are defined as major malformation overall, identified from child GP records up to 3 years old using Read codes which are mapped to the tenth edition of the International Classification of Diseases (ICD–10) code lists in EUROCAT (Table 1).(27) Five system-specific malformations (nervous, cardiovascular, digestive, genital tract, and urinary tract) were included which met the power criterion using the EUROCAT prevalence table.(29) (see “4.5 Power analysis”)

Table 1. Outcome identification.

Outcome	Case identification criteria
Cerebral palsy	Method based on predictor selection and prediction (23)
Epilepsy	2 prescriptions of antiepileptic drug (AED, identified based on British National Formula Chapter 4.8) within 4 months or ≥ 1 diagnosis

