4.3.3 Covariates

We will control the covariates which are potential risk factors for adverse child outcomes. These include: 1) maternal characteristics at baseline (i.e. age at child birth, problematic alcohol use, illicit drug use, recent tobacco use, and obesity); 2) pregnancy related variables (i.e. birth year, parity, multiple birth, hypertension, diabetes, epilepsy, depression, anxiety, maternal chronic medical conditions during pregnancy, potentially fetal-damaging maternal infection during pregnancy, and baby gender) (details given below). Gestational age at delivery and Apgar score after birth are considered mediators on the pathway for the association between prenatal antibiotics exposure and adverse child outcomes and therefore not adjusted.

1. *Maternal variables*

1) **Maternal age (at birth)**

By 5 year categories.

2) **Maternal life style:**

a. Problematic alcohol use:

Most recent record between 10 years prior to and during pregnancy:

- a Read code indicating alcohol misuse; or
- a prescription for disulfiram or acamprosate; or
- self-reported average weekly alcohol intakes of between 14-500 units of alcohol a week.

b. Illicit drug use:

Most recent record between 10 years prior to and during pregnancy:

- a read code for drug use, addiction, and overdose; or
- a prescription for methadone treatment

c. Recent smoking/tobacco use:

Most recent record between 3 years prior to and during pregnancy:

- self-reported daily cigarette consumption of 1-100 cigarettes per day unless there was evidence of smoking cessation; or
- a read code indicating tobacco consumption; or
- a prescription to assist smoking cessation

d. Obesity

Most recent record from 3 years prior to the end of 1st trimester:

A read code for obesity (or a BMI of ≥ 30 kg/m² - either directly entered or calculated from the most recent height measurement and median pre-pregnancy weight after outliers, i.e. height outside the range 1-2m and weight outside the range 35-300kg, were removed).

2. *Pregnancy related variables*

3) **Baby birth year**

Grouped into categories of 5 calendar years.

4) **Parity**

Categorised as "0", and " ≥ 1 ".

5) **Multiple births**

Categorize the baby as "singleton", or "(one of the) twin, triplets, or quadruplets".

6) **Hypertension**

Measurement from 50 weeks prior to delivery:

- systolic and diastolic blood pressure was above 140mmHg and 90mmHg, respectively, or

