4.4 Analyses

4.4.1 Statistical methods

Standardized differences will be used to assess covariate balance between the macrolides group and the penicillins group; meaningful imbalances are defined by an absolute standardized difference of more than 0.1.(30) For neurodevelopmental disorders, absolute rates of outcomes and unadjusted hazard ratios with 95% confidence intervals will be calculated. For malformations, absolute risks of outcomes and unadjusted risk ratios with 95% confidence intervals, will be calculated. Exposure propensity scores will be estimated as the predicted probability of receiving the macrolides prescription (vs. penicillins), conditional on the covariates described above, with the use of logistic-regression models. For each estimated propensity score, the population in the nonoverlapping areas of the propensity-score distributions will be trimmed, and 50 strata will be created on the basis of the distribution of the treated women.(31) Weights for the reference group will be calculated according to the distribution of the treated women among propensity-score strata. We then use the weight to estimate adjusted baseline characteristics, and adjusted hazard ratios (in Cox proportional hazard models with weight statement for neurodevelopmental disorders) or risk ratios (in log-binomial model with weight statement for malformations) as well as their 95% confidence intervals. To account for the clustering of siblings and multiple births within mother, robust standard errors will be estimated. The analyses will be conducted using RStudio version 3.5.1.. No adjustment will be made for multiple comparisons, and results for comparisons of exposure timing and subgroup analysis should be interpreted as exploratory.

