4.5 Power analysis

Initially interested outcomes include: cerebral palsy, epilepsy, ADHD, ASD, major malformation overall, and system-specific malformations according to the classification of EUROCAT.

To avoid spurious associations by chance we will restrict our analyses to outcomes which have >= 80% statistical power to detect a 2-fold relative risk increase at a 5% level of significance. Baseline risks of CP, epilepsy, ADHD, and ASD were calculated based on literature review and preliminary analyses, while the prevalence of major malformations (overall and system-specific) were based on the EUROCAT estimates.(29) The needed sample size of macrolides group was calculated for each outcome, based on a cohort of about 100,000 pregnancies exposed to penicillins (data from preliminary analyses). Preliminary analysis shows there are about 10,000 pregnancies in the macrolides group, therefore outcomes which requires more than 10,000 samples in macrolides group were excluded and will not be evaluated in this study (i.e. eye malformation, ear and face malformation, orofacial cleft, respiratory malformation, abdominal wall malformation and other malformation). Power calculations were performed using R package "pwr". (Figure 1 and Table 2)

Figure 1. Sample size estimation for macrolides group, n (penicillins) =100000, Sig=0.05, power=80%, risk ratio=2.

[figure not shown]

Table 2. Baseline risks and inclusion result for each outcome.

Outcome	Baseline Risk	Included
Cerebral palsy	0.002	Yes
Epilepsy	0.006	Yes
ADHD	0.006	Yes
ASD	0.008	Yes
Any major malformation	0.02	Yes
Cardiac malformation	0.007	Yes
Genital tract malformation	0.002	Yes
Urinary tract malformation	0.003	Yes
Gastrointestinal malformation	0.002	Yes
Nervous system malformation	0.002	Yes
Eye malformation	0.0003	No
Ear and face malformation	0.0001	No
Orofacial cleft	0.001	No
Respiratory system malformation	0.0004	No
Abdominal wall malformation	0.0005	No
Other malformation	<0.001	No

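### Birth year enters the propensity score only in 5-year bands, so calendar trends inside a band stay unadjusted; the likely bias is small and a spline removes most of it cheaply

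*Combined protocol and SAP*

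**What the plan says.** Section 4.2 defines the source population as "children born from Jan 1st 1990 to June 30th 2016", a span of 26.5 years touching 27 calendar years. Section 4.3.3, item 3, lists birth year as a covariate, "Grouped into categories of 5 calendar years". The first year of the first band is not stated.

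Section 4.4.1 estimates the propensity score "conditional on the covariates described above, with the use of logistic-regression models", so the model sees the bands only. After trimming, "50 strata will be created on the basis of the distribution of the treated women", and the reference group is weighted to match. On balance, "meaningful imbalances are defined by an absolute standardized difference of more than 0.1".

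Malformations are "identified from child GP records up to 3 years old using Read codes" (section 4.3.2) and analysed by a weighted log-binomial model. Follow-up ends on June 30th 2016 (section 4.2). Section 4.4.2 lists no analysis with a finer year term and none aimed at calendar time.

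**The concern.** Banding treats births up to five years apart as exchangeable on calendar time. If macrolide prescribing relative to penicillin and the recording of an outcome both move within a band, macrolide births sit at a different average date from the penicillin births they are weighted to match. Part of the calendar trend then appears as a drug contrast. The planned balance check would not reveal this, because the banded variable can be perfectly balanced while year within band is not.

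One such trend on the outcome side follows from the plan's own dates. Children born after June 2013 cannot reach age 3 by the end of follow-up, and those born in 2016 have less than six months. The chance of recording a malformation therefore falls with birth date inside the last band or bands, and a risk-ratio model has no person-time to absorb that. It becomes confounding only if macrolide share also drifts in those years.

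**Working it through.** **Inputs from the documents.** Births from January 1990 to mid-2016 (section 4.2). Group sizes from section 4.5: "Preliminary analysis shows there are about 10,000 pregnancies in the macrolides group", and the sample size was "based on a cohort of about 100,000 pregnancies exposed to penicillins". Baseline risks from Table 2: 0.02 any malformation, 0.008 ASD, 0.006 ADHD, 0.002 cerebral palsy.

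**The plan's own figure.** The documents give no figure for calendar confounding. Their related figure is the list of retained outcomes. The two-sided arcsine formula with 100,000 penicillin pregnancies, risk ratio 2 and 80% power requires 6,046 macrolide pregnancies at risk 0.002, 558 at 0.02 and 12,892 at 0.001. With a limit of 10,000 this matches Table 2, so the group sizes are used below.

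**Assumptions.** Uniform births; bands starting in 1990; macrolide share of 10% in 2003; log-odds of macrolide changing by g per year; log outcome risk changing by b per year; no true drug effect.

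**How much the bands remove.** The variance of birth year is 58.6 in total and 1.90 within bands. 1.90/58.6 = 3.2%, so the bands remove about 97% of it.

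**Residual bias.** Penicillin births are standardised to the macrolide distribution, and the ratio of mean risks is taken:

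| g, b per year | No year adjustment | 5-year bands | Single year |
|---|---|---|---|
| 0.05, 0.05 | 1.144 | 1.004 | 1.000 |
| 0.05, 0.10 | 1.276 | 1.008 | 1.000 |
| 0.10, 0.10 | 1.555 | 1.016 | 1.000 |
| 0.15, 0.15 | 2.203 | 1.032 | 1.000 |
| 0.20, 0.15 | 2.608 | 1.042 | 1.000 |

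Hand check: within a band the bias is about exp(g × b × Var), with Var = (25 − 1)/12 = 2 for five equal years. For 0.10 and 0.10 that is exp(0.02) = 1.020, close to the pooled 1.016. Moving the first band year changes 1.016 to between 1.015 and 1.019, and 1.042 to between 1.038 and 1.055.

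**Abrupt change.** If macrolide share and recorded risk both step up after the second year of one band, the bias in that band is 1.04 (both × 1.5) to 1.11 (both × 2), diluted when bands are pooled. The documents describe no such joint step. The only dated change in an outcome definition is the post-2005 exclusion of minor anomalies in Table 1.

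**Truncated malformation window.** Assume recording accrues linearly to age 3. Mean available follow-up is 2 years for 2014 births (2/3 ascertained), 1 year for 2015 (1/3) and 0.25 year for 2016 (0.083). With no other risk trend:

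| g per year | Bands from 1990 | Last band 2012–2016 |
|---|---|---|
| +0.05 | 0.998 | 0.994 |
| +0.10 | 0.994 | 0.983 |
| −0.05 or −0.10 | 1.001 | 1.002 |

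If half of malformations are recorded at birth and the rest accrue linearly, the +0.10 results become 0.997 and 0.992.

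**Against sampling error.** SE of the log ratio is √(1/200 + 1/2,000) = 0.074 for any malformation and √(1/80 + 1/800) = 0.117 for ASD. The 10%/10% bias is ln(1.016) = 0.016, about 0.2 and 0.1 SE. The 95% interval factor at the null, exp(1.96 × SE), is 1.16 for any malformation, 1.26 for ASD, 1.30 for ADHD and 1.58 for cerebral palsy.

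**The case against.** The strongest reply is that birth year is already adjusted for, that the bands remove nearly all of its variance, and that the documents show no trend in either macrolide share or recording. Confounding needs both trends in the same band. All of this stands and limits the point to a refinement.

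The negative control cohort in section 4.4.2 compares the same drugs for the same outcomes before conception, so a shared calendar trend would tend to appear there. That stands too, but the analysis would detect the problem and not correct it, and its stated target is maternal baseline characteristics.

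Stronger readings are tempting:

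- A reader might infer that drift appears as a drug effect in every outcome and exposure window. Nothing in the documents shows this; it is conditional, outcome by outcome.
- A reader might infer a bias of 6%, since a single five-year band with 20% and 15% drift gives 1.059. That is not a pooled estimate. Sustained over 26.5 years, those rates imply macrolide odds growing exp(0.20 × 26.5) ≈ 200-fold and outcome risk exp(0.15 × 26.5) ≈ 53-fold.
- A reader might place all the truncated births in one latest band and add their effect to that of rising recording. Band boundaries are not stated. Bands from 1990 would split these births over two bands, and when macrolide share rises the truncation effect is below 1, against the other.
- A reader might infer that finer coding costs nothing. Indicators carry a modest cost in the smaller analyses.

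**Conclusion.** The point holds as a minor one. Within-band calendar imbalance is unadjusted, the planned balance check on the banded variable cannot see it, and no listed analysis corrects it. At assumed drifts of 5 to 10% per year in both macrolide share and recorded risk, the residual bias is about 0.4 to 1.6%. It is about 4% in the extreme 20%/15% case, somewhat more under some band starts.

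Truncation of the age-3 window shifts the malformation risk ratio by about 1% or less in most settings tried. The largest shift at 10% drift was 1.7%, with linear accrual and a last band of 2012–2016.

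Every drift rate, the accrual pattern and the band boundaries are assumptions. The sizes are small against the confidence intervals and against the risk ratio of 2 used for power, so this would not be expected to change a conclusion. It is worth fixing because the bias does not shrink with sample size and the remedy is slight. Finer year coding makes ascertainment opportunity comparable between groups; it does not complete the missing follow-up to age 3.

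**What to change.** In section 4.3.3, item 3, state that birth year enters the propensity model as a restricted cubic spline. Single-year indicators are an alternative in the whole-pregnancy analysis, where numbers allow. Keep the 5-year categories for the baseline table and state their boundaries.

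In section 4.4.1, add a balance check on single year, done within bands. Over the whole cohort, a 10% drift leaves a mean difference of about 0.10 × 1.90 = 0.19 year. Divided by an SD of √58.6 = 7.65, this gives 0.025, which passes the 0.1 rule. Within a five-year band the same drift gives about 0.10 × √2 = 0.14, which does not.

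Cost: a line or two of SAP wording and no new data. A spline adds a few parameters. Indicators add about 21 (26 for 27 calendar years, against 5 for six bands), with on average 10,000/26.5 ≈ 377 macrolide and 100,000/26.5 ≈ 3,774 penicillin pregnancies per year. The first-trimester, azithromycin and duration analyses have no stated sizes; indicators there could be sparse and increase trimming, so use the spline.

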4.3 Study Variables

4.3.1 Exposure

The exposure group will include children whose mother were prescribed an only monotherapy of macrolide antibiotics from 5 GW to delivery (hereafter, “during pregnancy”). A monotherapy is defined as one or more consecutive prescriptions for a single antibiotic (i.e. same drug substance) separated by no more than 30 days and uninterrupted by prescriptions for other antibiotic drug substances. The macrolides prescription is identified using a drug code list based on chapter 5.1.5 of the British National Formulary. The date of first prescription is used as the index date. The reference group includes children whose mothers were exposed to an only monotherapy of penicillins during pregnancy. Preliminary analysis shows that 81% of all antibiotic prescriptions were monotherapies. We further divide the time window into 1) 5GW to 13GW (29 Gestational Day [GD] to 91GD, hereafter, “1st trimester”), the critical period for most major malformation, and 2) 14GW to delivery (hereafter, “2nd–3rd trimester”).(21) The negative control cohort (see “4.4.2 Sensitivity analyses [1]”) includes children of mothers prescribed an only monotherapy of macrolides or penicillins during 10-50 weeks prior to conception and are not included in the study cohort.

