- a Read codes for hypertension and associated diagnoses (including pre-eclampsia, eclampsia and HELLP syndrome), or
- a prescription for hypertension drugs from sections 2.2 and 2.5 of the BNF. This variable identified mothers with both treated and untreated hypertension in pregnancy.

7) **Diabetes**

Measurement from 50 weeks prior to delivery:

- a Read code for type I, type II, or gestational diabetes;
- two or more prescriptions for anti-diabetic medication; or
- laboratory tests indicative of diabetes (defined as ≥ 2 abnormal glucose tests, fasting glucose >7.0 millimoles per litre [mmol/L] or >126 milligrams per decilitre

[mg/dL], plasma glucose after glucose tolerance test >11.1 mmol/L or 200mg/dL, glycated haemoglobin \geq 6.5%, or with diabetes annual review).

8) Epilepsy

Measurement from 50 weeks prior to delivery: 2 prescriptions of antiepileptic drugs (AEDs) within 4 months or \geq 1 diagnosis

9) Depression

Measurement from 50 weeks prior to delivery: \geq 2 occurrences of diagnostic code, treatment code or symptom

10) Anxiety

Measurement from 50 weeks prior to delivery: \geq 2 occurrences of diagnostic code, treatment code or symptom

11) Treatment of chronic medical conditions during pregnancy

Measurement during pregnancy: two or more prescriptions (on separate days during pregnancy and not more than four months apart) for drugs from the same BNF section or paragraph. Drugs used to treat common conditions in pregnancy such as reflux (BNF section 1.2), nausea and vomiting (BNF section 4.6), and constipation (BNF section 1.3) were not included.

12) Potentially fetal-damaging infections during pregnancy.

Mothers are classified as having a potentially fetal-damaging infection in pregnancy if they had recorded at any time during their pregnancy, a Read code for a diagnosis or a laboratory test confirming any of the following infection: genitourinary infection, "TORCH" (Toxoplasmosis, Other agents such as HIV, Rubella, Cytomegalovirus and Herpes simplex) and sexually transmitted infections (STIs). "TORCH" and STIs have long been known as important risk factors to adverse pregnancy outcomes and teratogenic pathogens. (22, 23) Intrauterine infection has been recognised as an important mechanism of disease in preterm labor. (24) Hyelonephritis and bacteriuria have also been linked with preterm labor and low birthweight. (25)

3. Neonatal variables

13) Baby gender

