Appendix

A hierarchy of available pregnancy markers was chosen that reflects their potential accuracy to estimate start of the pregnancy episode. Pregnancy markers that directly provide gestational age such as gestational age in weeks, prenatal examination, and fertility procedures (IVF) were on the top of the hierarchy. Next hierarchy of markers include ranges of gestational week indicators (e.g. premature 24-26 weeks) and outcome-specific estimates (e.g. premature labour, imputed as 36 weeks, because around 60% live premature births born at 36 gestational weeks). Gestational weeks imputed from birthweight was on the 3rd hierarchy, based on the intrauterine growth curves published by Irene E. Olsen et al.(32) For pregnancies with no information available for the above three hierarchies of markers, full term births were assumed and gestational week 40 were used to calculate pregnancy start dates. Codes used in each hierarchy is referenced from Matcho, A. et al. (33)

For babies in the Mother-baby link, gestational age were measured from each hierarchy with the following proportion: 27.8% from the first hierarchy (from codes for gestational age), 14.3% from the second hierarchy (from codes for gestational week range), 8.2% from the third hierarchy (imputed based on birthweight), 49.6% (imputed as full term, 40 gestational weeks). The proportion of preterm birth was 6.2% preterm births in general populations, which is marginally lower than reported by the Office for National Statistics (7.1%).(34) The potentially underestimated proportion of preterm births would over-record antibiotic exposure during the early pregnancy, which would bias the association towards null.

Reference

1. Agency MHPR. Package leaflet: Information for the user: Clarithromycin 250 mg Film-Coated Tablets 2016 [Available from: <http://www.mhra.gov.uk/home/groups/spcpil/documents/spcpil/con1507872162573.pdf>.
2. Britain; JFCG. British National Formulary. Pharmaceutical Press; 2016. p. 307.

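### Five maternal conditions in the macrolide propensity score have no cut-off at the index date, so conditions first recorded after the prescription can be balanced as if they were baseline

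*Combined protocol and SAP*

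**What the plan says.** Section 4.3.3 gives one time rule for items 6 to 10 (hypertension, diabetes, epilepsy, depression, anxiety): "Measurement from 50 weeks prior to delivery". No end date is written. The hypertension definition accepts codes for pre-eclampsia, eclampsia and HELLP syndrome, and the diabetes definition accepts gestational diabetes. Depression and anxiety each need at least two records.

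Three other passages bear on this:

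- Section 4.2 requires that the mother "had been registered with GP from at least 50 weeks before estimated conception date to delivery".
- Section 4.3.1 states: "The date of first prescription is used as the index date". Exposure can start at 5 GW.
- Section 4.3.3 leaves two post-exposure variables unadjusted: "Gestational age at delivery and Apgar score after birth are considered mediators on the pathway".

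Section 4.4.1 conditions the propensity score on all listed covariates and describes the weighted output as adjusted baseline characteristics.

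**The concern.** A propensity score for choosing a macrolide over a penicillin should use what was known when the prescription was written. A condition first recorded weeks later cannot have influenced that choice, but it may be a consequence of the infection or of the drug. Balancing the arms on it can remove part of an effect or introduce bias of its own. The plan accepts this reasoning for gestational age and Apgar score, but gives no reason for treating later pre-eclampsia or gestational diabetes differently.

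The first-trimester comparison leaves the most time for such records. It is listed under the primary analyses in 4.4.2, although 4.4.1 asks that comparisons of exposure timing be read as exploratory. The negative control analysis is also affected: its prescriptions fall 10-50 weeks before conception, so much or all of the covariate window follows them.

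**Working it through.** **Inputs.** The covariate window is 50 weeks (4.3.3), and the guaranteed pre-conception registration is 50 weeks (4.2). The first-trimester exposure window is "5GW to 13GW (29 Gestational Day [GD] to 91GD" (4.3.1). Negative-control exposure is 10-50 weeks before conception (4.3.1). Forty weeks is the Appendix default where no gestational marker exists: "full term births were assumed and gestational week 40 were used to calculate pregnancy start dates". The interval c from pregnancy start to conception is not given, so I assume 0 to 2 weeks and show both ends.

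**The plan's own figure.** Start of 5 GW = (5 - 1) x 7 + 1 = GD 29. End of 13 GW = 13 x 7 = GD 91. Both agree with 4.3.1.

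**Reading (a), literal: the window opens 50 weeks before delivery and runs to delivery.** Pre-conception weeks used = 50 - (GA - c). Share after the index date = (GA - GD/7)/50.

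| Gestation at birth (weeks) | Pre-conception weeks used | Share after index at GD 29 | Share after index at GD 91 |
|---|---|---|---|
| 28 | 22-24 | 47.7% | 30.0% |
| 36 | 14-16 | 63.7% | 46.0% |
| 40 | 10-12 | 71.7% | 54.0% |

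For 40 weeks and GD 29: (40 - 29/7)/50 = 35.9/50 = 71.7%. For GD 91: (40 - 13)/50 = 27/50 = 54.0%. The share reaches 50% at GD (40 - 25) x 7 = 105. Unused guaranteed pre-conception history at 40 weeks is 50 - 12 = 38 to 50 - 10 = 40 weeks.

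**Reading (b): 50 weeks before conception through to delivery.** Pre-conception weeks are 50 for every mother. Share after the index date = (GA - GD/7)/(50 + GA - c). At 40 weeks:

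- GD 29: 35.9/90 = 39.8% (c = 0) to 35.9/88 = 40.7% (c = 2).
- GD 91: 27/90 = 30.0% to 27/88 = 30.7%.

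**Negative control.** Under (a) at 40 weeks, the window opens 10-12 weeks before conception. So 50 - 12 = 38 to 50 - 10 = 40 of the 40 exposure weeks lie wholly before it.

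**Closing the window at the index date instead.** With c = 2, the length runs from 50 + 29/7 - 2 = 52.1 weeks (index at GD 29) to 50 + 38 = 88 weeks (index close to a 40-week delivery). In the negative control cohort it runs from 40 weeks down to 0.

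**Fixed window, 50 weeks before conception to GD 28.** Length = 50 + 4 - c = 52 weeks (c = 2) to 54 weeks (c = 0), the same for every mother under a given c. Share after a study-cohort index date = 0. For a negative-control prescription w weeks before conception, the share after it is (w + 4 - c)/(54 - c):

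- w = 10: 12/52 = 23% to 14/54 = 26%.
- w = 30: 32/52 = 62% to 34/54 = 63%.
- w = 50: 100%.

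**The case against.** The strongest reply is that the wording has two readings. The obesity item is phrased in a parallel way (a span before, then an end point), and a 50-week look-back from conception is exactly what the registration rule secures. Under reading (b), nothing is discarded and look-back does not vary with gestation. This stands, so the delivery anchor cannot be treated as established, although it is the plainer text.

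A reader might infer that the plan throws away guaranteed history, that ascertainment depends on gestational length, and that most of the window follows early exposure. The first two hold only under (a). Even there the total is always 50 weeks and only the split around conception moves. The Appendix also limits how many births this concerns: "The proportion of preterm birth was 6.2% preterm births in general populations", and the largest group by source of gestational age is "49.6% (imputed as full term, 40 gestational weeks". The third fails under (b). Under (a) it fails for late first-trimester exposure in 36-week births and for any first-trimester exposure in 28-week births.

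It can also be said that measurement during pregnancy is deliberate. Section 4.3.3 files these items under pregnancy-related variables and describes the hypertension item as covering hypertension in pregnancy. The window is the same in both arms, and item 11 already captures repeat prescribing for chronic disease. That is a fair reason to keep an analysis that balances pregnancy conditions, but it does not make records made after the prescription part of baseline.

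Finally, closing the window at the index date has its own faults: look-back would vary with prescription timing, and would be empty for the earliest negative-control prescriptions. That objection is correct, and the change below avoids it.

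**Conclusion.** The point holds on either reading, provided the window runs to delivery: items 6-10 can carry information recorded after the index date into the propensity score, including conditions that begin in pregnancy. For a first-trimester prescription and a 40-week birth, 54-72% of the window follows the prescription on the literal reading and 30-41% on the alternative. These are shares of calendar time, not of recorded diagnoses. They assume conception 0 to 2 weeks after pregnancy start.

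The documents give no frequency of post-index diagnoses and no association with exposure or outcome. Neither the size nor the direction of any bias can therefore be derived, and it would be wrong to conclude that the hazard or risk ratios are distorted by a known amount. The case for change is that a clean pre-exposure window is available from data the eligibility rule already requires.

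**What to change.** - **Main propensity score.** In 4.3.3, items 6-10, state start, anchor and end: from 50 weeks before estimated conception to the end of 4 GW (GD 28). Because the window and the exposure period use the same estimated dates, it closes before every index date in the study cohort even where gestation is imputed.
- **Sensitivity analysis.** Keep the current window through delivery, with its start stated explicitly.
- **Negative control cohort.** Apply the same fixed window for comparability. State that it largely follows exposure there, because look-back before the prescription is not guaranteed for prescriptions near 50 weeks before conception.
- **Other covariates.** Review items 11 and 12, alcohol, drug use and smoking, which also run into pregnancy. Obesity closes at the end of the first trimester, which can also follow an early index date.

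The cost is a wording change and a re-run of covariate extraction on records already held. The downside is that conditions first recorded after 4 GW, including long-standing ones recorded late, are no longer balanced in the main model. The sensitivity analysis would show whether that matters.
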